8.6.2. Clinical Laboratory Parameters

All clinical laboratory parameters, their changes from baseline will be listed, as applicable; any value outside the clinical reference range will be flagged. Separate listings will be provided for any parameter for which there is any individual subject value outside the respective clinical reference range.

Summary tables by group treatment sequence and timepoint will be provided for clinical chemistry, hematology parameters, their changes from baseline as applicable.

Where data available, shifts from baseline tables will be provided for clinical chemistry and hematology parameters.

Values recorded as $< x$, $\leq x$, $> x$, or $\geq x$ will be displayed in the listings as recorded. For the derivation of listing flags, all calculations, and presentation in the figures, $< x$ and $\leq x$ values will be set to 0, whereas $> x$ and $\geq x$ values will be set to x .

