3. STUDY ENDPOINTS

Electrocardiogram Endpoints:

The primary endpoint is the change-from-baseline QTcF (Δ QTcF).

The secondary endpoints are:

- Change-from-baseline HR, PR, QRS (Δ HR, Δ PR, and Δ QRS);
- Placebo-corrected change-from-baseline HR, QTcF, PR, and QRS ($\Delta\Delta$ HR, $\Delta\Delta$ QTcF, $\Delta\Delta$ PR, and $\Delta\Delta$ QRS);
- Categorical outliers for QTcF, HR, PR, and QRS;
- Frequency of treatment-emergent changes of T- wave morphology and U-wave presence.

Pharmacokinetic Endpoints:

- area under the concentration-time curve from time zero extrapolated to infinity (AUC_{inf})
- area under the concentration-time curve from time zero to 24 hours postdose (AUC_{0-24})
- maximum observed concentration (C_{max})
- time of the maximum observed concentration (t_{max})

Other PK parameters may also be reported.

Safety Endpoints:

The safety outcome measures for this study are as follows:

- incidence and severity of AEs
- incidence of laboratory abnormalities, based on hematology, clinical chemistry, and

urinalysis test results

- 12-lead ECG parameters
- vital signs measurements.

Note: This SAP only focuses on the PK, safety and tolerability endpoints. All QTc related endpoints will be covered in a separate report provided by ERT Inc.

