8. STATISTICAL METHODOLOGY

8.1. General

Listings will be provided for all data captured in the database, including medical history. Listings will include all subjects assigned to the all subjects population and include data up to the point of study completion or discontinuation. Subjects are generally considered to have completed the study if they complete the scheduled follow-up visit (rather than early termination visit). Any subject who discontinues the study will be identified accordingly in the listings. Summaries and statistical analyses will include the subjects assigned to the relevant population based on data type.

Data analysis will be performed using the SAS® statistical software package Version 9.4 (or higher if a new version is issued during the study).

Analysis Data Model (ADaM) datasets will be prepared using Clinical Data Interchange Standards Consortium (CDISC) ADaM Version 2.1 (or higher if a new version is issued during the study) and CDISC ADaM Implementation Guide Version 1.1 (or higher if a new version is issued during the study). Pinnacle 21 Community Validator Version 3.1.0 (or higher if a new version is issued during the study) will be utilized to ensure compliance with CDISC standards.

Where reference is made to 'valid' data, this refers to non-missing data which meet the predetermined criteria (eg, are not flagged for exclusion).

Where reference is made to 'all calculations', this includes, but is not limited to, summary statistics, statistical analyses, baseline derivation and changes from baseline.

All figures will be produced on linear-linear or discrete-linear scales, as applicable, unless specifically stated otherwise.

8.1.1. Handling of Data Quality Issues Due to Coronavirus Disease 2019 and Related Restrictions

Due to COVID-19 and related restrictions, there is a high risk for impact to data integrity, with the recognized potential for:

- Missed visits, caused by, for example,:
 - Subject unable to travel to site due to restrictions, the need to quarantine, or COVID-19 infection
 - Subject unwilling to go to site due to fear of COVID-19 infection
 - Site postponing subject's visit due to investigator not being available (eg, if they have been dispatched to hospital handling COVID-19 infections)
- Site unable to replenish supply of investigational product
- Incomplete data entry by sites due to limited resources to support study or no access to source documents or to eCRF

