8.6.7. Safety and Tolerability Statistical Methodology

No inferential statistical analysis is planned.

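### Laboratory range flags are derived from substituted numbers, which can give wrong flags when the reporting limit lies at or inside the reference limits

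*SAP*

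**What the plan says.** SAP Section 8.6.2 covers results that the laboratory gives only as an inequality. In the listings they "will be displayed in the listings as recorded". A substituted number is used "For the derivation of listing flags, all calculations, and presentation in the figures". Results of the form `<x` and `≤x` "values will be set to 0, whereas" those of the form `>x` and `≥x` take the value x.

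The reach of the rule follows from three other statements:
- Section 8.1 says that references to all calculations cover at least "summary statistics, statistical analyses, baseline derivation and changes from baseline".
- Section 8.6.2 says that "any value outside the clinical reference range will be flagged". It also plans separate listings for any parameter that has an out-of-range value.
- Section 8.6.2 says that "shifts from baseline tables will be provided for clinical chemistry and hematology parameters".

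Section 3 names as a safety outcome the "incidence of laboratory abnormalities, based on hematology, clinical chemistry, and" urinalysis results. Section 8.6.7 adds: "No inferential statistical analysis is planned".

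**The concern.** A range flag should follow from what the laboratory reported. Under this rule it follows from a number that the laboratory did not report, and the two can disagree. The rule is also asymmetric. On the low side it takes the most extreme value compatible with the result, and on the high side the least extreme.

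The outputs at stake describe a named safety outcome. The out-of-range listings are triggered by out-of-range values, so a missed High can keep a parameter off its listing and a false Low can put one on. Urinalysis has no planned summary or shift table in Section 8.6.2, so its flagged listings are the only planned output. For chemistry and hematology the substituted numbers also enter means and changes from baseline. The SAP does not say separately how shift categories are derived, but on its present wording they would come from the same numbers.

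**Working it through.** The plan states no figure on this point, so there is none to reproduce. The check applies the rule case by case and compares its flag with every flag that the true value could have.

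**Inputs.** The substitution rule and its scope come from Sections 8.6.2 and 8.1. The SAP gives no reporting limits or reference ranges, so the following are assumptions for illustration only: lower limit 0 or 3, upper limit 20, and the values of x. True values are taken as non-negative. A value is Low if below the lower limit and High if above the upper limit; a value equal to a limit is in range.

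**Low side (rule: `<x` and `≤x` become 0).**

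| Lower limit | Result | Flag by the rule | Flags the true value allows |
|---|---|---|---|
| 0 | `<2`, `<3`, `<5` (and the `≤` forms) | none | none |
| 3 | `<2`, `≤2` | Low | Low |
| 3 | `<3` | Low | Low |
| 3 | `≤3` | Low | Low or none |
| 3 | `<5`, `≤5` | Low | Low or none |

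**High side (rule: `>x` and `≥x` become x; upper limit 20).**

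| Result | Flag by the rule | Flags the true value allows |
|---|---|---|
| `>15`, `≥15` | none | High or none |
| `>20` | none | High only |
| `≥20` | none | High or none |
| `>40`, `≥40` | High | High |

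The `>20` row is wrong with certainty. In the `≤3`, `<5`, `≤5`, `>15`, `≥15` and `≥20` rows the rule gives one fixed flag although the report leaves the flag open.

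**Change from baseline, with x = 3.**
- Baseline 4, later `<3`: the rule gives 0 − 4 = −4. The true change lies between 0 − 4 = −4 and 3 − 4 = −1. Substituting x would give −1, and x/2 would give 1.5 − 4 = −2.5.
- Baseline `<3`, later 4: the rule gives 4 − 0 = +4. The true change lies between 4 − 3 = +1 and 4 − 0 = +4. Substituting x would give +1, and x/2 would give 4 − 1.5 = +2.5.

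Where one of the two results is `<x` and the other is measured above x, zero therefore gives the largest change the data allow. On the high side it is the reverse: for baseline 18 and later `>20` the rule gives 20 − 18 = +2, while the true change is more than +2. If both results are `<x`, the rule gives a change of 0.

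**The case against.** The strongest reply is that nothing in the SAP shows that any analyte in this trial meets the conditions for a wrong flag. If the lower limit is 0 or absent, zero is never flagged. If `<x` has x at or below a positive lower limit, the Low flag is right. If x exceeds the upper limit, `>x` is still flagged High. This stands, and it is why the point is conditional.

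Second, a reader of the listings sees the inequality itself, the safety analysis is descriptive, the same substitution applies in every group, and the QTc analysis is untouched. This stands as a limit on the consequences. It does not repair the flags, the selection of parameters for the out-of-range listings, or the means.

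Third, zero is a familiar convention. The SAP itself uses it for concentrations below quantification in PK summaries (Section 8.5.2). Those values, however, are not compared with a reference range. The cardiodynamic plan (its Section 6.1) uses half the lower limit of quantitation for post-dose CBP-307 values, so zero is not forced. Any single substitute leaves some bias, and the choice between x and x/2 is partly a preference. That part of the objection stands.

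A reader might go further and infer that the rule does produce false Low abnormalities in this trial, in some countable number per group, or that it inflates the variability of changes by a known amount. The documents do not support this. They give neither the share of censored results nor where x lies relative to the ranges. A Low flag on a censored result is not in itself false, and a subject censored at both visits has a change of 0.

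**Conclusion.** The rule as written can contradict the laboratory's own report, but only where x lies at or inside the reference limits:
- `>x` with x equal to the upper limit is never flagged High, although every possible true value is high.
- `>x` with x below the upper limit, or `≥x` with x at or below it, can miss a true High.
- `<x` with x above a positive lower limit, or `≤x` with x at or above it, is always flagged Low, although the true value may be in range.

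Separately, zero is the most extreme value compatible with `<x`, so falls from an uncensored baseline are overstated, while rises that end in `>x` are understated.

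The number of results affected cannot be estimated from the SAP and may be zero. These conclusions rest on the rule taken literally and on limits counted as in range; the effect on shift tables is inferred. This is a minor point, worth correcting because it bears on a named safety outcome and costs little.

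**What to change.** Amend Section 8.6.2 in two places.

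1. **Flags, out-of-range listings and shift categories.** Derive all three from the result as reported, or from the laboratory's own flag:
   - `<x` is Low if x is at or below the lower limit.
   - `≤x` is Low if x is below the lower limit.
   - `>x` is High if x is at or above the upper limit.
   - `≥x` is High if x is above the upper limit.

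   The shift tables need to be named. If they were built from a substituted x, a result `<3` with lower limit 3 would be Low in the listing and normal in the shift table.

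2. **Summary statistics and change from baseline.** Replace 0 with one prespecified value tied to the reporting limit, either x or x/2, and use it throughout.

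The cost is two SAP sentences and a small change to the flag derivation. Two limits remain. Means of censored values keep some bias whichever substitute is chosen. A result whose possible values straddle a reference limit, such as `<5` with lower limit 3, gets no flag under the four conditions, so the SAP should say so or rely on the laboratory's flag there. Where no such results occur, nothing changes.

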8.6.3. Vital Signs Parameters

All vital signs parameters, their changes from baseline will be listed, as applicable; any value outside the clinical reference range will be flagged.

Summary tables by group treatment sequence and timepoint will be provided for all vital signs parameters, their changes from baseline, as applicable.

Where data available, shifts from baseline tables will be provided for vital sign parameters.

8.6.4. Safety 12-lead Electrocardiogram Parameters

All 12-lead ECG parameters, their changes from baseline, will be listed; any value outside the clinical reference range will be flagged.

Summary tables by group treatment sequence and timepoint will be provided for all 12-lead ECG parameters, their changes from baseline.

Where data available, shifts from baseline tables will be provided for 12-lead ECG parameters.

An outlier analysis will be performed for QT interval corrected for heart rate using Bazett's formula (QTcB) and QT interval corrected for heart rate using Fridericia's formula (QTcF). The analysis will include all individual original, repeat, and unscheduled postdose values.

The maximum postdose values will be summarized by treatment according to the following categories:

- ≤ 450 ms
- >450 and ≤ 480 ms (all instances flagged in the listing)
- >480 and ≤ 500 ms (all instances flagged in the listing)
- >500 ms (all instances flagged in the listing)

The maximum increases from baseline will be summarized by treatment according to the following categories:

- ≤ 30 ms
- >30 and ≤ 60 ms (all instances flagged in the listing)

>60 ms (all instances flagged in the listing)

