8.1.2. Calculation of the Summary Statistics

For continuous data the following rules will be applied:

- Missing values will not be imputed, unless specifically stated otherwise.
- Unrounded data will be used in the calculation of summary statistics.
- If the number of subjects with valid observations (n) <3, summary statistics will not be calculated, with the exception of n, minimum, and maximum.
- In general, as early termination data are not associated with any scheduled timepoint, they will be excluded from all calculations of summary statistics and statistical analyses. Exceptions may be made where justified.

For categorical data the following rules will be applied:

- For ordered categorical data (eg, adverse event [AE] severity), all categories between the possible minimum and maximum categories will be included, even if n = 0 for a given category.

- For non-ordered categorical data (eg, race), only those categories for which there is at least 1 subject represented will be included; unless specifically stated otherwise.
- Missing values will not be imputed, unless specifically stated otherwise. A ‘missing’ category will be included for any parameter for which information is missing. This will ensure that the population size totals are consistent across different parameters.

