8.1.4. Repeat and Unscheduled Readings

For vital signs and 12-lead ECG data only, any predose value recorded in addition to the original value or a postdose value recorded within 15 minutes of the original value will be defined as a repeat value; any postdose value recorded more than 15 minutes after the original value will be defined as an unscheduled value. For all other data types (eg, laboratory parameters), any value recorded in addition to the original value will be defined as an unscheduled value.

As unscheduled values are not associated with any scheduled timepoint, they will be excluded from all calculations unless specifically stated otherwise.

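### The safety QTc outlier analysis does not name early-termination ECGs, so the SAP's default leaves them out of a table that uses no timepoint

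*SAP*

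**What the plan says.** Four places in the main SAP bear on this.

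- **Section 8.1 (General)** foresees an early termination visit that is distinct from scheduled follow-up: "Subjects are generally considered to have completed the study if they complete the scheduled follow-up visit (rather than early termination visit").
- **Section 8.1.2**, in a rule introduced as general, says that "as early termination data are not associated with any scheduled timepoint, they will be excluded from all calculations of summary statistics and statistical analyses". It then adds "Exceptions may be made where justified", with no criterion and no named case.
- **Section 8.1.4** has a separate rule for unscheduled readings: "As unscheduled values are not associated with any scheduled timepoint, they will be excluded from all calculations unless specifically stated otherwise".
- **Section 8.6.4** states otherwise for the QTcB/QTcF outlier analysis: "The analysis will include all individual original, repeat, and unscheduled postdose values". On the output it says: "The maximum postdose values will be summarized by treatment according to the following categories". The categories are cut at 450, 480 and 500 ms. Maximum increases from baseline are treated in the same way, with cuts at 30 and 60 ms.

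**The concern.** The SAP has two kinds of ECG record without a scheduled timepoint, unscheduled and early-termination, and excludes both by default for the same reason. For the outlier table it lifts the exclusion for the first kind and says nothing about the second. A reader who applies the text as written would leave out the exit ECG of a subject who stops early.

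This table is the main SAP's summary of extreme safety QTc values, in a study whose purpose is to assess QTc. Records missing because of withdrawal are not a random subset. If the exit ECG holds a subject's highest QTc, the table would place that subject in too low a category.

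**Working it through.** The point concerns which records enter the analysis. The SAP gives no figure to reproduce, so the check sets the rules side by side.

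**Step 1: how each type of postdose ECG is treated**

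| Record type | Default rule | Reason given | Outlier analysis (8.6.4) |
|---|---|---|---|
| Original | Included | – | Included |
| Repeat | Defined in 8.1.4; no exclusion stated there | – | Included |
| Unscheduled | Excluded (8.1.4) | No scheduled timepoint | Included by name |
| Early termination | Excluded in general (8.1.2) | No scheduled timepoint | Not mentioned |

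The last two rows share a default and a reason. They differ only in the final column.

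**Step 2: does the reason apply to this table?** A summary by timepoint cannot place a value that has no timepoint, so exclusion makes sense there. The outlier table takes a maximum over postdose values and reports it by treatment, so it needs no timepoint. Restoring unscheduled values fits this logic. The SAP gives no ground for treating early-termination values differently.

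**Step 3: direction of the effect.** Let A be a subject's admitted postdose QTc values under a treatment, and x the exit value. Then max(A ∪ {x}) ≥ max(A). The same holds for increases, since the baseline is fixed. For each threshold (450, 480 or 500 ms; 30 or 60 ms), adding x can leave the number of subjects above it unchanged or raise it by one, and can never lower it. A middle category can lose a subject, but only to a higher one. For example, a subject whose highest admitted value is above 450 and up to 480 ms, with an exit value above 500 ms, moves from the second category to the fourth.

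**Step 4: what stays visible.** Section 8.6.4 also says "All 12-lead ECG parameters, their changes from baseline, will be listed; any value outside the clinical reference range will be flagged". It requires flags in the listing for all instances above 450 ms and all increases above 30 ms. The exit value would therefore be reported, but as a listing entry and not in the summary.

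**The case against.** A reader might infer that the SAP bars an exit ECG from ever counting as an outlier. The documents do not support that, for two reasons.

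- The rule in 8.1.2 is general and open to exceptions, and a maximum-value table is an obvious candidate for one. This stands. What remains is that no exception is written down. Inclusion could then be decided after the value is known, although the SAP is meant to be final before unblinding.
- Section 8.1.4 says that, for vital signs and ECGs, "any postdose value recorded more than 15 minutes after the original value will be defined as an unscheduled value". An exit ECG could be read into that definition and so enter through 8.6.4. The reading is possible but strained: an exit ECG has no original value at its own timepoint to be compared with, and the reading would make the separate early-termination rule largely redundant for ECGs. The rule in 8.1.2 also sits under continuous data, while the outlier table is categorical. If more than one reading is tenable, two programmers could produce different counts, which is itself a reason to settle the wording.

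A reader might also try to size the problem from the 34 subjects randomized and 28 evaluable per group. The documents do not present that gap as a withdrawal allowance, and a subject can be non-evaluable without withdrawing. Other figures in the document point elsewhere: main SAP Section 5 gives 32 per group, and the quality tolerance limit is 64 evaluable subjects.

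The consequence is also limited. The value is listed and flagged, and adverse events leading to discontinuation are summarized separately. The categorical QTcF analysis in Section 6.4 of the cardiodynamic SAP is a separate analysis, and Section 8.6.7 plans no inferential safety analysis. All of this stands.

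**Conclusion.** The point holds as a modest one. By default, and subject to unspecified exceptions, early-termination ECGs are left out of the safety QTcB/QTcF outlier analysis, for a reason that does not apply to it. The omission can only keep or lower the number of subjects above each threshold. It reaches one descriptive safety analysis and no primary or inferential result. Its numerical size cannot be derived from the documents.

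The conclusion rests on two assumptions. The first is that a 12-lead safety ECG is recorded at the early termination visit: the SAP mentions the visit but not its assessments, and the protocol is not at hand. The second is that an exit ECG is not already treated as an unscheduled value. If it is, the counts are complete and only the wording needs attention.

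**What to change.** 1. In Section 8.6.4, state that the outlier analysis includes *all individual original, repeat, unscheduled and early-termination postdose values*.
2. In Section 8.1.2, name this analysis as an exception to the exclusion of early-termination data.
3. Attribute early-termination ECGs to treatment by the same rule used for unscheduled ECGs in this table. A rule based on the last active treatment would not do: Group 2A receives moxifloxacin only on Day 1 and placebo afterwards, so an exit ECG taken on a later placebo day would be counted under moxifloxacin.

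The cost is one phrase in 8.6.4, one in 8.1.2 and one filter in the program. The only downside is that outlier counts may rise slightly.

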4. STUDY DESIGN

This will be a Phase I, randomized, double-blind, double-dummy, placebo-controlled, positive-controlled, multi-site, 3-arm study to investigate the effects of therapeutic and supratherapeutic oral doses of CBP-307 on the QTc interval in healthy male and female subjects.

Potential subjects will be asked to read and sign an informed consent form (ICF). After informed consent is obtained, screening procedures and tests to establish subject eligibility to enter the study will be performed within 28 days before Day 1. After informed consent has been obtained but prior to the initiation of study treatment administration, only SAEs will be reported. After placebo administration to all subjects on Day -1, all AEs, whether volunteered, elicited, or noted upon physical examination, will be recorded throughout the study (ie, from Day -1 until the end of the study).

In this study, approximately 68 healthy subjects (at least 30% for each sex) will be randomized into 2 groups (Group 1 and 2) with 34 subjects in each. Group 2 consists of 2 sub-groups (Group 2A and 2B) and each sub-group will be randomized with 17 subjects. Randomized subjects will receive the assigned study drug as a single dose in the morning on Days 1, 2, 3 to 6, 7 to 15, and on Day 16 (placebo will be administered to all subjects on Day -1).

The following treatments will be administered:

- Starting doses of CBP-307 for titration (0.05 mg on Day 1 followed by an up-titrated dose of 0.1 mg on Day 2)
- A therapeutic dose of CBP-307 (0.2 mg, Days 3 to 6)
- A supratherapeutic dose of CBP-307 (0.5 mg, Days 7 to 15)
- Placebo (matched to moxifloxacin and CBP-307)
- Moxifloxacin (400 mg)

Moxifloxacin will be used as a positive control to determine the assay sensitivity of this study with an expected peak QT effect (placebo-corrected change-from-baseline QTcF; $\Delta\Delta QTcF$) of 10 to 15 msec.

[figure not shown]
A summary of dosing timelines per Group is shown below:

Study Treatment Name	Treatment Group	CBP-307	CBP-307 Matched Placebo	Moxifloxacin (Avelox)	Moxifloxacin Matched Placebo
Dosage Formulation		Capsule	Capsule	Tablet	Tablet
Unit Dose Strength(s)/Level(s)		0.05 mg 0.1 mg	Not applicable	400 mg	Not applicable
Dosage Frequency					
Day -1	Group 1 Group 2A Group 2B		1 capsule 1 capsule 1 capsule		
Day 1	Group 1 Group 2A Group 2B	1 × 0.05 mg		1 × 400 mg	1 tablet 1 tablet
Day 2	Group 1 Group 2A Group 2B	1 × 0.1 mg			
Days 3 to 6	Group 1 Group 2A Group 2B	2 × 0.1 mg			

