6. STUDY TREATMENTS

The study treatment names and ordering to be used in the TFLs are presented in [Table 1](#).

Table 1: Presentation of Study Treatments in TFLs

Study Treatment	Order in TFLs
Placebo	1
400 mg Moxifloxacin	2
0.05 mg CBP-307	3
0.1 mg CBP-307	4
0.2 mg CBP-307	5
0.5 mg CBP-307	6

All TFLs will be based on actual treatments (eg, if subject was assigned to receive placebo but was wrongfully dosed with active treatment they would be summarized and listed under active treatment).

The study treatment sequence names, abbreviations, and ordering to be used in the TFLs are presented in [Table 2](#).

Table 2: Presentation of Study Treatment Sequences in TFLs

Study Treatment Sequence	Abbreviation	Order in TFLs
1 capsule of CBP-307 matched placebo on Day -1 -> 1 × 0.05 mg CBP-307 and 1 tablet of Moxifloxacin matched placebo on Day 1 -> 1 × 0.1 mg CBP-307 on Day 2 -> 2 × 0.1 mg CBP-307 on Days 3 to 6 -> 5 × 0.1 mg CBP-307 on Days 7 to 15 -> 1 capsule of CBP-307 matched placebo and 1 tablet of Moxifloxacin matched placebo on Day 16	Group 1	1
1 capsule of CBP-307 matched placebo on Day -1 -> 1 capsule of CBP-307 matched Placebo and 1 × 400 mg Moxifloxacin tablet on Day 1 -> 1 capsule of CBP-307 matched Placebo on Day 2 -> 2 capsules of CBP-307 matched Placebo Days 3 to 6 -> 5 capsules of CBP-307 matched Placebo on Days 7 to 15 -> 1 capsule of CBP-307 matched placebo and 1 tablet of Moxifloxacin matched placebo on Day 16	Group 2A	2
1 capsule of CBP-307 matched placebo on Day -1 -> 1 capsule of CBP-307 matched Placebo and 1 tablet of Moxifloxacin matched placebo on Day 1 -> 1 capsule of CBP-307 matched Placebo on Day 2 -> 2 capsules of CBP-307 matched Placebo Days 3 to 6 -> 5 capsules of CBP-307 matched Placebo on Days 7 to 15 -> 1 capsule of CBP-307 matched placebo and 1 × 400 mg Moxifloxacin tablet on Day 16	Group 2B	3

The summaries will be based on planned treatment sequences and listings will be based on actual treatment and sequences.

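### The safety QTc outlier table compares per-subject maxima between treatment labels that cover unequal numbers of days, so its columns differ even with no drug effect

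*SAP*

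**What the plan says.** SAP Section 8.6.4 plans an outlier analysis of the safety ECGs for QTcB and QTcF. Two per-subject maxima are put into categories: "The maximum postdose values will be summarized by treatment according to the following categories" and "The maximum increases from baseline will be summarized by treatment according to the following categories". The readings that enter are broad: "The analysis will include all individual original, repeat, and unscheduled postdose values".

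Table 1 in Section 6 lists six treatment labels, with a single Placebo row. Sections 4 and 6 fix how long each label lasts. Titration is "0.05 mg on Day 1 followed by an up-titrated dose of 0.1 mg on Day 2", followed by 0.2 mg on Days 3 to 6 and 0.5 mg on Days 7 to 15. Group 2 takes placebo over the same period, including "5 capsules of CBP-307 matched Placebo on Days 7 to 15", apart from one moxifloxacin day (Day 1 in Group 2A, Day 16 in Group 2B). In addition, "placebo will be administered to all subjects on Day -1", and Group 1 receives placebo again on Day 16.

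Section 8.6.4 sets no day window for a treatment, gives no ECG count as a denominator, and has no rule for assigning an ECG to a treatment. The other safety-ECG summaries in that section are by group treatment sequence and timepoint; only the outlier tables are by treatment label.

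**The concern.** The maximum of several readings tends to be higher than the maximum of few. If one column gives each subject one day in which to produce a high QTc and another gives fifteen, the second will show more outliers even if neither treatment does anything.

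Two distortions follow. Placebo, the reference column, tends to look worse than the short-duration doses. Within CBP-307, the counts tend to climb from 0.05 mg to 0.5 mg because the dosing periods lengthen in that order. A reader of the clinical study report could take the first as reassurance and the second as a dose response. Neither inference would be sound.

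**Working it through.** The plan states no figure for this table, so there is nothing to reproduce. The check counts days from the plan and then shows the effect of the count under stated assumptions.

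**Days per label (SAP Sections 4 and 6).**
- CBP-307 0.05 mg: Day 1 = 1. 0.1 mg: Day 2 = 1. 0.2 mg: Days 3–6 = 4. 0.5 mg: Days 7–15 = 9.
- Moxifloxacin: 1.
- Placebo, Group 2A: Days 2–16 = 15. Group 2B: Days 1–15 = 15. Each is 16 if Day -1 counts.
- Ratio of placebo days to CBP-307 days: 15/1, 15/1, 15/4 = 3.75 and 15/9 = 1.67.

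**Absolute value above 450 ms.** Assumptions, none of them from the plan: one ECG per dosing day, no drug effect, subject mean m distributed N(415, 15²), within-subject error SD 8 ms. For k readings,

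P(max > 450) = average over m of 1 − Φ((450 − m)/8)^k.

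For k = 1 this has a closed form: total SD = √(15² + 8²) = 17, (450 − 415)/17 = 2.06, upper tail 2.0%. Numerical integration gives:

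| Readings k | Label | Share > 450 ms | Expected subjects in 34 |
|---|---|---|---|
| 1 | 0.05 mg, 0.1 mg | 2.0% | 0.7 |
| 4 | 0.2 mg | 4.8% | 1.6 |
| 9 | 0.5 mg | 7.1% | 2.4 |
| 15 | Group 2 placebo | 8.9% | 3.0 |

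(34 per group is the figure in SAP Section 4.) Placebo against 0.5 mg is 3.0 − 2.4 = 0.6 subject.

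Other inputs move the level but not the order. Mean 400 ms, between-subject SD 15 and within-subject SD 8 give 0.16%, 0.47%, 0.79% and 1.06%. Mean 410 ms with SDs 18 and 10 gives 2.6%, 6.2%, 9.3% and 11.5%.

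**Increase above 30 ms.** With independent baseline and postdose errors, each has SD s = (SD of change)/√2, and P(max increase > 30) = average over z ~ N(0,1) of 1 − Φ((30 + s·z)/s)^k.

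| SD of change | k = 1 | k = 4 | k = 9 | k = 15 |
|---|---|---|---|---|
| 8 ms | 0.01% | 0.03% | 0.07% | 0.12% |
| 10 ms | 0.14% | 0.50% | 1.0% | 1.5% |
| 12 ms | 0.6% | 2.1% | 4.1% | 5.9% |

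The 8 ms is the SD of ΔQTcF assumed in SAP Section 5 for the core-laboratory ECGs. The 10 and 12 ms rows are assumptions that allow for noisier safety ECGs. At 8 ms the expected count at k = 15 is 34 × 0.12% = 0.04 subject, which is negligible.

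**How far the result depends on rules that are not stated.**
- If safety ECGs fell only on Days 1, 6, 15 and 16, Group 2 placebo would have 3 readings against 1 each for 0.05, 0.2 and 0.5 mg. In the 415 ms example that is 4.1% against 2.0%, with no built-in trend among those three doses.
- The only by-treatment window in the SAP is for adverse events (Section 8.6.1), where 0.5 mg runs from Day 7 to the end of study. Follow-up is Day 29 ± 2, so the span is 29 − 7 + 1 = 23 days, more than the 15 placebo days of Group 2B before its moxifloxacin. Subjects leave the unit on Day 19, so the number of ECGs in that span is unknown.
- If the Placebo row also took in one Day 16 reading from each Group 1 subject, it would average 34 subjects at k = 15 and 34 at k = 1: (8.9% + 2.0%)/2 = 5.4%, below the 7.1% for 0.5 mg.

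**The case against.** The best case against the point is that the plan gives dosing days and not ECG counts. Section 4 says only that safety ECGs are taken at specific timepoints, and the table shells are a separate document. That is right, and it limits what can be claimed. A reader might infer that every CBP-307 dose is set against a placebo column with far more ECGs, so that a signal at 0.5 mg would be hidden. The document does not support this. For 0.5 mg the dosing-day ratio is 15 to 9, the illustrated gap is about 0.6 subject, and the direction could reverse under other assignment rules. What remains is that the windows are unequal and undefined.

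Safeguards also exist. Section 8.6.7 plans no inference. Section 8.6.4 flags every reading above 450 ms, and every increase above 30 ms, in the listings, and gives day-matched summaries by sequence and timepoint. The cardiodynamic SAP has its own QTcF outlier analysis, with subject and time-point percentages (Section 6.4) and day-specific placebo sets (Section 5.3, Table 3). These limit the consequence. They do not make the columns of this table comparable, and it is the only outlier table described for QTcB.

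It is also tempting to ask that the maxima use scheduled ECGs only. Section 8.1.4 excludes unscheduled values unless stated otherwise, and Section 8.6.4 makes a deliberate exception so that a high reading is not lost. That choice should stand.

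**Conclusion.** The point holds at low severity. As written, Section 8.6.4 yields outlier columns built on observation windows of 1, 1, 4 and 9 days for CBP-307, 1 day for moxifloxacin and 15 to 16 days for Group 2 placebo, with no rule linking an ECG to a treatment. With no drug effect, placebo tends to look worse than the short-duration doses and the CBP-307 columns tend to rise with dose.

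The size is conditional on one ECG per dosing day and on assumed QTc distributions. The share above 450 ms goes from about 2% with one reading to about 9% with fifteen in the main example. The share with an increase above 30 ms at fifteen readings is about 0.1%, 1.5% or 5.9% for an SD of change of 8, 10 or 12 ms. The distortion is greatest for the one-day titration doses and small for 0.5 mg. The primary concentration-QTc conclusion is not affected.

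**What to change.** In Section 8.6.4, tabulate the maximum values and maximum increases by group within the same day windows: Day 1, Day 2, Days 3–6 and Days 7–15. Place Group 1 beside concurrent Group 2 placebo in each window, leaving out Group 2A on Day 1 because that day is moxifloxacin. State the rule that assigns an ECG to a window, including ECGs taken after Day 15, and show the number of ECGs per subject in each column. Keep repeat and unscheduled values in the maxima, as the plan states; the ECG count then shows any remaining imbalance.

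With matched windows, scheduled ECG counts are equal on both sides, and the expected outlier share with no drug effect is the same apart from repeat and unscheduled readings. The cost is wording in the SAP and the table shells, with no new data. The downside is a longer table with smaller cells; in the Day 1 window the placebo comparator is Group 2B alone, 17 subjects.
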